## 2.4 Treatments (study treatment, rescue medication, concomitant therapies, compliance)

### 2.4.1 Study treatment / compliance

The FAS will be used for the analyses below. Categorical data will be summarized as frequencies and percentages. For continuous data, mean, standard deviation, median, 25th and 75th percentiles, minimum, and maximum will be presented.

The duration of exposure in months to Dabrafenib and Trametinib respectively, as well as actual cumulative dose, the dose intensity (DI) (computed as the ratio of actual cumulative dose received and actual duration of exposure) and the relative dose intensity (RDI) (computed as the ratio of dose intensity and planned dose intensity) will be summarized by means of descriptive statistics. Duration of exposure will be categorized into time intervals; frequency counts and percentages will be presented for the number(%) of subjects in each interval. The number (%) of subjects who have dose changes, reductions or interruptions, and the reasons, will be summarized.

### **Dose exposure and intensity**

Definitions of duration of exposure, cumulative dose, average daily dose, dose intensity (DI), relative dose intensity (RDI), as well as intermediate calculations, include:

- Duration of exposure (days): last date of study drug – first date of study drug + 1 (periods of interruption are not excluded)
- Cumulative dose (mg): total dose of study drug taken by a patient in the study
- Number of dosing days (days): duration of exposure – number of zero dose days
- Average daily dose (mg/day): cumulative dose (mg)/number of dosing days (days)
- DI (mg/day): cumulative dose (mg)/duration of exposure (days)
- RDI (%):  $100 \times [DI \text{ (mg/day)} / \text{planned dose}]$

The number of subjects with dose adjustments (reductions, interruption, or permanent discontinuation) and the reasons will be summarized and all dosing data will be listed.

Summary statistics of time to first dose reduction / interruption will also be presented.

Subject level listings of all doses administered on treatment along with dose change reasons will be produced.

### **Dose reductions, interruptions or permanent discontinuations**

The number of subjects who have dose reductions, permanent discontinuations or interruptions, and the reasons, will be summarized.

‘Dose changed’, ‘Dose interrupted’, and ‘Dose permanently discontinued’ fields from the Dosage Administration CRF pages (DAR) will be used to determine the dose reductions, dose interruptions, and permanent discontinuations, respectively.

The corresponding fields ‘Reason for dose change/dose interrupted’ and ‘Reason for permanent discontinuation’ will be used to summarize the reasons.

A dose change is either ‘change in prescribed dose level’ or ‘dosing error’ where actual dose administered/total daily dose is different from the prescribed dose.

For the purpose of summarizing interruptions and reasons, in case multiple entries for interruption that are entered on consecutive days with different reasons will be counted as separate interruptions. However, if the reason is the same in this block of entries, then it will be counted as one interruption.

**Reduction:** A dose change where the prescribed dose level is lower than the previous prescribed dose level or where the actual dose administered/total daily dose is lower than the calculated dose amount based on the prescribed dose. Therefore any dose change to correct a dosing error will not be considered a dose reduction. Number of reductions will be derived programmatically based on the change and the direction of the change.

The number of subjects who continue treatment beyond RECIST1.1 progression according to local investigators assessment based on protocol specified criteria will be summarized. It includes all subjects who received any study treatment (i.e. at least one dose of any component of the study treatment) after RECIST 1.1 progression assessed by local investigators. Those subjects will be identified using the field “Will the subject continue treatment beyond disease progression as per RECIST1.1?” on the Verification for Treatment beyond RECIST1.1 PD CRF pages.

#### **2.4.2 Prior, concomitant and post therapies**

##### **Prior anti-cancer therapy**

The number and percentage of patients who received any prior anti-neoplastic medications, prior anti-neoplastic radiotherapy or prior anti-neoplastic surgery, will be summarized by treatment group and overall. Prior anti-neoplastic medications will be summarized by therapy type (e.g. chemotherapy, hormonal therapy, immunotherapy etc.) and setting (e.g. adjuvant, metastatic, etc.). Summaries will also include total number of regimens, time from last treatment to progression for the last therapy, type of therapy received at any time or as last systemic therapy for metastatic lung cancer prior to enrollment, excluding radiotherapy and surgery, best response to last systemic therapy based on RECIST v1.1. The medication therapy type of any combination therapy will be classified based on the types of treatment taken at each regimen. For example, a combination therapy of targeted therapy and immunotherapy will be classified in both categories with appropriate sub-types.

For radiotherapy, time since last radiotherapy, locations and setting of last therapy will be summarized. For prior surgery, time since last surgery and procedure will be summarized.

Separate listings will be produced for prior anti-neoplastic medications, radiotherapy, and surgery. Palliative antineoplastic radiotherapy administered during the treatment phase may also be summarized.

Anti-neoplastic medications will be coded using the WHO Drug Dictionary (WHO-DD); anti-neoplastic surgery will be coded using MedDRA. Details regarding MedDRA and WHO-DD version will be included in the footnote in the tables/listings.

The above analyses will be performed using the FAS.

##### **Concomitant medications**

Concomitant therapies are defined as any medications (excluding study drug, prior antineoplastic treatments and blood transfusions), surgeries or procedures (including physical therapy) administered in the study and are recorded in the Prior and Concomitant Medications and the Surgical and Medical Procedures eCRF, respectively.

Concomitant medications will be coded using the WHO Drug Reference Listing (WHO DRL) dictionary that employs the WHO Anatomical Therapeutic Chemical (WHO ATC) classification system. Surgeries or procedures will be coded using the Medical Dictionary for Regulatory Activities (MedDRA) terminology. All summaries will be tabulated using frequency counts and percentages.

Concomitant therapies will be summarized by ATC class and preferred term. These summaries will include: 1) medications starting on or after the start of study drug but starting no later than 30 days after last dose of study drug and 2) medications starting prior to the start of study drug but continuing after the start of study drug.

All concomitant therapies will be listed. Any concomitant therapies starting and ending prior to the start of study drug or starting more than 30 days after the last date of study drug will be flagged in the listings.

## **2.5 Analysis of the primary objective**

The primary objective is to assess the ORR of dabrafenib in combination with trametinib in Chinese patients with *BRAF* V600E mutation-positive metastatic NSCLC by central independent assessment.

### **2.5.1 Primary endpoint**

The primary endpoint of the study is overall response rate (ORR), defined as the proportion of subjects with best overall response (BOR) of complete response (CR) or partial response (PR), as per central independent review assessment and according to RECIST 1.1.

### **2.5.2 Statistical hypothesis, model, and method of analysis**

This study will pursue an estimation approach rather than formal hypothesis testing. The ORR will be summarized along with its exact 95% confidence intervals.

### **2.5.3 Handling of missing values/censoring/discontinuations**

Subjects in the study who are of unknown clinical response will be treated as non-responders.

## **2.6 Analysis of secondary efficacy objective(s)**

The secondary efficacy objectives in this study are: To assess overall response rate (ORR), progression-free survival (PFS), duration of response (DoR) and overall survival (OS) by investigator assessment.

### **2.6.1 Secondary endpoints**

All secondary efficacy assessments (ORR, PFS, DoR, OS) will be analyzed as per investigator assessment. Confirmation of response is required for all response endpoints, as per RECIST 1.1.

All secondary efficacy analyses will be performed based on the FAS.

The secondary efficacy endpoints are:

- ORR

- PFS
- DoR
- OS

## **2.6.2 Statistical hypothesis, model, and method of analysis**

ORR is defined as the percentage of subjects with a confirmed complete response (CR) or partial response (PR) by investigator assessment as per RECIST 1.1 criteria. ORR will be analyzed in the FAS population. ORR will be summarized along with its exact 95% confidence intervals.

PFS is defined as the time from the date of first dose to the date of the first documented progression or death due to any cause. PFS will be assessed via local review according to RECIST 1.1. PFS will be censored if no PFS event is observed before the first to occur between: (i) the analysis cut-off date, and (ii) the date when a new anti-neoplastic therapy is started. The censoring date will be the date of the last adequate tumor assessment prior to cut-off/start of new anti-neoplastic therapy.

PFS will be analyzed in the FAS population. The PFS distribution will be estimated using the Kaplan-Meier method, and the Kaplan-Meier curves, medians and 95% confidence intervals of the medians will be presented, if appropriate.

Duration of response (DoR) only applies to subjects whose best overall response is complete response (CR) or partial response (PR) according to RECIST 1.1 based on tumor response data per local review. The start date is the date of first documented response of CR or PR (i.e. the start date of response, not the date when response was confirmed), and the end date is defined as the date of the first documented progression or death due to any cause. Subjects continuing without progression or death will be censored at the date of their last adequate tumor assessment. DoR will be listed and summarized for all subjects in the FAS with confirmed BOR of CR or PR.

OS is defined as the time from date of first dose to date of death due to any cause. If a subject is not known to have died, then OS will be censored at the latest date the subject was known to be alive (on or before the cut-off date).

OS will be analyzed in the FAS population. The OS distribution will be estimated using the Kaplan-Meier method, and the Kaplan-Meier curves, medians and 95% confidence intervals of the medians will be presented, if appropriate.

## **2.6.3 Handling of missing values/censoring/discontinuations**

For subjects who have not progressed or died at the time of the PFS, OS or DoR analysis, censoring will be performed using the date of the last adequate disease assessment or first dose for subjects without any adequate post baseline assessments. In addition, subjects with a loss to follow-up prior to a PFS or death event will be censored at the date of the last adequate disease assessment prior to the loss to follow-up for PFS or OS, respectively. Subjects who start new anti-cancer therapy prior to a PFS event will be censored for PFS and DoR (if this subject is a responder). In these cases, an adequate assessment is defined as an assessment where the investigator determined response is CR, PR, or SD.

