12.5.1 Efficacy endpoint(s)

ORR is defined as the percentage of participants with a confirmed complete response (CR) or partial response (PR) by investigator assessment as per RECIST 1.1 criteria. ORR will be analyzed in the FAS population. ORR will be summarized along with its exact 95% confidence intervals.

PFS is defined as the time from the date of first dose to the date of the first documented progression or death due to any cause. PFS will be assessed via local review according to RECIST 1.1 (see [Section 16](#) for further details). PFS will be censored if no PFS event is observed before the first to occur between: (i) the analysis cut-off date, and (ii) the date when a new anti-neoplastic therapy is started. The censoring date will be the date of the last adequate tumor assessment prior to cut-off/start of new anti-neoplastic therapy.

PFS will be analyzed in the FAS population. The PFS distribution will be estimated using the Kaplan-Meier method, and the Kaplan-Meier curves, medians and 95% confidence intervals of the medians will be presented, if appropriate.

Duration of response (DOR) only applies to participants whose best overall response is complete response (CR) or partial response (PR) according to RECIST 1.1 based on tumor response data per local review. The start date is the date of first documented response of CR or PR (i.e. the start date of response, not the date when response was confirmed), and the end date is defined as the date of the first documented progression or death due to any cause. Participants continuing without progression or death will be censored at the date of their last adequate tumor assessment. DOR will be listed and summarized for all participants in the FAS with confirmed BOR of CR or PR.

OS is defined as the time from date of first dose to date of death due to any cause. If a participant is not known to have died, then OS will be censored at the latest date the participant was known to be alive (on or before the cut-off date).

OS will be analyzed in the FAS population. The OS distribution will be estimated using the Kaplan-Meier method, and the Kaplan-Meier curves, medians and 95% confidence intervals of the medians will be presented, if appropriate.

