16.1.3.2.2 Overall survival

All patients should be followed until death or until patient has had adequate follow-up time as specified in the protocol whichever comes first. The follow-up data should contain the date the patient was last seen alive / last known date patient alive, the date of death and the reason of death (“Study indication” or “Other”).

Overall survival (OS) is defined as the time from date of randomization/start of treatment to date of death due to any cause. If a patient is not known to have died, survival will be censored at the date of last known date patient alive.

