- Date of discontinuation is the date of the end of treatment visit.
- Date of last contact is defined as the last date the patient was known to be alive. This corresponds to the latest date for either the visit date, lab sample date or tumor assessment date. If available, the last known date patient alive from the survival follow-up page is used. If no survival follow-up is available, the date of discontinuation is used as last contact date.
- Date of secondary anti-cancer therapy is defined as the start date of any additional (secondary) antineoplastic therapy or surgery.

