#### **2.1.1.5 Last contact date**

Last contact date will be used for the censoring of patients in the analysis of overall survival.

The last contact date will be derived for patients not known to have died at the analysis cut-off using the last complete date among the following:

- Last contact date collected on the 'Survival information' eCRF.
- All assessment dates (e.g. tumor assessment, laboratory/PK collection dates, vital signs assessment, performance status, ECG assessment). Note, only a true on study assessment date or patient contact date will be used. If there is a visit date without evidence of any actual assessment performed that date will not be used. No dates post cut-off will be used.
- Medication dates including study medications, concomitant medications, and anti-cancer therapies administered after study treatment discontinuation.
- Adverse event dates.

Note: The cut-off date will not be used for last contact date, unless the patient was seen or contacted on that date.

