## **5 Appendix**

### **5.1 Imputation rules**

In general imputed partial dates will not be used to derive study day, duration (e.g. duration of adverse events), or elapse time variables. In addition, imputed dates are not used for deriving the last contact date in overall survival analysis dataset.

Imputed dates will not be displayed in listings. However, where necessary, display macros may impute dates as temporary variables for the purpose of sorting data in listings only. In addition, partial dates may be imputed for 'slotting' data to study time periods or for specific analysis purposes as outlined below.

The partial date imputation will follow Analysis Data Model (ADaM) conventions. The ADaM approach is to populate the numeric date variables with the imputed date and add a flag variable to the dataset that indicates the level of imputation. The flag variable can contain the values: blank, 'D', 'M', 'Y'.

blank: indicates that no imputation was done

D='Day': indicates that the day portion of the date is imputed

M='Month': indicates that the month and day portions of the date are imputed

Y='Year': indicates that the entire date (year, month, and day) is imputed.

Details on imputing partial dates for specific datasets are outlined in following sections.

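### SAP 2.6.3 censors overall survival at the last adequate tumor assessment for two groups of subjects, against the last-known-alive rule in SAP 2.6.2, SAP 2.1.1.5 and the protocol; the likely effect is small

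*SAP*

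**What the plan says.** SAP 2.6.3 mentions OS twice.

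- First sentence: "For subjects who have not progressed or died at the time of the PFS, OS or DoR analysis, censoring will be performed using the date". That date is the subject's most recent adequate scan, with first dose as the fallback when no adequate post-baseline scan exists.
- Second sentence: for anyone whose follow-up is lost before progression or death, the rule is that they "will be censored at the date of the last adequate disease assessment prior to the loss to follow-up for PFS or OS, respectively".

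The same paragraph defines an adequate assessment as one with an investigator response of CR, PR or SD.

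Elsewhere the rule for OS is different. SAP 2.1.1.5 states: "Last contact date will be used for the censoring of patients in the analysis of overall survival". It then lists the sources of that date: survival form, assessments, medication dates and adverse event dates. SAP 2.6.2 and protocol 12.5.1 censor at the latest date known alive, up to cut-off. Protocol Appendix 16.1.3.2.2 says: "If a patient is not known to have died, survival will be censored at the date of last known date patient alive". SAP 5.1 presupposes the same variable: "imputed dates are not used for deriving the last contact date in overall survival analysis dataset". SAP Section 4 reports no departure from the protocol analysis.

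**The concern.** For the two groups named in 2.6.3, the SAP gives two censoring dates for one endpoint, and a programmer cannot use both. Section 2.6.3 is the section headed as dealing with censoring, so following it would be a reasonable choice. The SAP was last updated for the final analysis, where OS will be reported.

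The scan-based date is also the wrong one for OS. A subject who progressed and was later lost has no CR, PR or SD scan after progression. Everything learned from the 3-monthly survival contacts (protocol 9.1.2) would be dropped. A living, progression-free subject with no adequate post-baseline scan would be censored for OS at first dose. At stake are the OS curve, its median and its landmark estimates.

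**Working it through.** **1. The passages side by side**

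| Place | OS censoring date if not known to have died |
|---|---|
| SAP 2.6.3, sentence 1 (not progressed or died) | Last CR/PR/SD assessment, else first dose |
| SAP 2.6.3, sentence 2 (lost to follow-up) | Last CR/PR/SD assessment before loss |
| SAP 2.6.2 | Latest date known alive |
| SAP 2.1.1.5 | Last contact date |
| Protocol 12.5.1 | Latest date known alive |
| Protocol Appendix 16.1.3.2.2 | Last date known alive |

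The protocol appendix (16.1.3.2.8) keeps the two dates apart. "Date of last contact is defined as the last date the patient was known to be alive", while the last adequate tumor assessment is tied to CR, PR or SD. Appendix 16.1.4.5.6 lists only being alive and being lost to follow-up as censoring reasons for survival.

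Read literally, subjects who have progressed, are alive and are still followed fall outside 2.6.3 and stay under 2.6.2.

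**2. Direction**

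The Kaplan-Meier estimate is the product over death times of (1 − d/n). If all known deaths are kept, 2.6.3 only moves censoring times earlier. Each d is unchanged and each n is the same or smaller, so every factor, and the curve, is lower or unchanged wherever it is estimated. In simulation the 24-month estimate was higher under 2.6.3 in 0% of trials.

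The exception is a subject who was lost and later found to have died. If sentence 2 is used to censor that subject, an event is removed. Protocol 9.1.2 ends survival follow-up at loss, so this has little scope.

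**3. Loss of follow-up time for one subject (illustration)**

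Suppose SD at week 30, progression at week 36, three further 3-monthly survival contacts, then loss. Time discarded = 6 weeks + 9 months = 1.4 + 9 = 10.4 months.

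**4. Size by simulation**

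The documents give no OS figure or loss rate, so there is no planned value to reproduce. There were 6,000 trials of 40 per scenario, with a Monte Carlo standard error of at most 0.03 points.

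Inputs from the documents:
- Scans every 6 weeks to week 36, then every 12 weeks (protocol 8.3.1).
- Visits every 3 weeks (Table 8-1) and survival contacts every 3 months (9.1.2).
- Study end 17 months after the last patient's first visit (9.2).
- Entry A, from amendment dates, with month 0 = 08-Jun-2020: 20 subjects by month 9.1 and 14 over months 16.2-33.1, which is 14/16.9 = 0.83 per month. The last 6 enter at the same rate, to month 40.4 (assumed).
- Entry B, planned 12 + 12 months (4.1): months 0-12 and 16.2-28.2.

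Assumptions: exponential PFS with median 10 months (protocol 1.2 cites 9.7 and 10.9); 10% of PFS events are deaths; exponential post-progression survival with median 8, 12, 18 or 24 months; exponential loss. Proportion lost by 24 months = 1 − exp(−24 × monthly rate).

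| Monthly loss | Lost by 24 months | Mean fall in 24-month OS (points) | Fall in median OS (months) |
|---|---|---|---|
| 0 | 0% | 0.1-0.5 | 0.0-0.3 |
| 0.5% | 11% | 1.0-1.3 | 0.3-1.3 |
| 1% | 21% | 1.6-2.4 | 0.5-2.4 |
| 2% | 38% | 2.9-4.4 | 0.9-4.0 |

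The SD of the 24-month estimate across trials is 7.5-10.1 points, and every mean fall is below half of one SD.

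With no loss, about 4-6 of 40 subjects are affected and each loses about 1 month. At 1% monthly loss, 7-9 of 40 are lost; 2-4 of these had documented progression and lose on average 8-13 months each.

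For example, with entry A and 1% loss, median OS under last contact and under 2.6.3 is 20.4 and 19.9 months (post-progression median 8), or 35.3 and 32.9 (post-progression median 24).

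**5. Second set of runs with other inputs**

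PFS median was 10 or 15 months, post-progression median 8 or 15, and loss was set per year. The mean fall in 24-month OS was 0.4-0.7 points with no loss, 1.0-1.1 at 5%, 1.5-1.7 at 10% and 2.3-3.1 at 20%. For scale, the 95% half-width at 56% survival is 1.96 × √(0.56 × 0.44/40) = 15.4 points.

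**The case against.** The strongest reply is that the intended rule is plain. SAP 2.1.1.5 is devoted to it, SAP 2.6.2 and 5.1 agree, and the protocol states it in three places. Section 2.6.3 reads like PFS text into which OS was carried by accident, so most programmers would use last contact. OS is descriptive in a single-arm estimation study. This limits the seriousness of the point, but it does not reconcile the two rules.

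The literal reading can also be questioned. Sentence 1 could be taken endpoint by endpoint, so that for OS it covers everyone still alive. That ambiguity is real. Under this wider reading the second set of runs gives a fall in median OS of 1.8-5.9 months, so the small effect reported here depends on the narrower reading.

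The size also depends on scans being done on schedule and being evaluable. If progression-free subjects stop scans but remain in survival follow-up, contrary to protocol 9.1.1, the median falls by about 0.7-3.5 months at 5% yearly loss. With a PFS median of 15 months, 8-11 of 40 subjects are affected without any loss. In the other direction, 2% monthly loss is hard to square with the due diligence required by protocol 9.1.4.

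Entry A lets the first 20 subjects enter right up to the primary cut-off, although two post-baseline scans were needed by then. Ending that block 12 weeks earlier, near month 6.3, leaves the results essentially unchanged.

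**Conclusion.** The concern holds. SAP 2.6.3 is wrong as written for OS, and it conflicts with two other SAP sections and with the protocol without a declared change. That conclusion rests on the text alone.

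The size rests on assumed loss and survival. On the literal reading with all known deaths kept, 24-month OS is understated on average by at most half a point without loss to follow-up and by about 2 points at 1% monthly loss, which is small against the noise of 40 subjects. A single trial can move more: at 10% yearly loss, 19-24% of simulated trials shifted the median by more than 1 month.

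The downward direction fails if known deaths after loss are removed. If 25% of such deaths become known by cut-off and are censored under sentence 2 (entry A, 1% loss), the mean fall shrinks to 1.3-1.8 points and the estimate is higher under 2.6.3 in 16-23% of trials. The primary ORR is not touched.

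**What to change.** Delete OS from both sentences of SAP 2.6.3 and keep the last-adequate-assessment rule for PFS and duration of response only. State that OS is censored at the last contact date of SAP 2.1.1.5, on or before cut-off, including for subjects lost to follow-up. Add that any death known to have occurred on or before cut-off is an event even after loss. SAP 2.6.2 already implies this, but saying it closes the one route by which an event could be removed. The cost is SAP wording only, with no new data.
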